60 hospitalisation, and mortality (2). A representative population study in the United States reported
61 a frailty prevalence of 15% amongst community-dwelling older adults (3). Meanwhile, a study of
62 older adults conducted based on the United Kingdom (UK) biobank reported 39% as prefrail and
63 4% as frail. Similar trends are observed in Singapore, an Asian island-state of 5.7 million (4),
64 which is also one of the most rapidly ageing countries in the world (5). The reported prevalence
65 of frailty in Singapore ranged from 5.7% to 6.2% with corresponding 37% to 46% for pre-frailty
66 (6-8) among community-dwelling older adults, depending on the population studied and
67 identification tool used (9).

68 Frailty can be managed and even reversed (10). With almost 40% of our population assessed
69 as frail or in danger of becoming frail, there is a strong need to equip the Singapore healthcare
70 system to identify and manage frailty (11). In order to accomplish this whilst addressing the
71 complex care needs of frail older adults, care has shifted from a disease-specific to a
72 comprehensive approach (12). Comprehensive care for frail older adults usually comprises several
73 components, including comprehensive geriatric assessments (CGAs), multidisciplinary teams,
74 integrated care plans and a variety of services to cater to the healthcare and social needs of these
75 frail older adults (13). Screening for frailty can identify individuals who are most likely to benefit
76 from a CGA and targeted interventions (14). In 2017, England became the first in the world to
77 mandate the assessment of frailty in adults aged 65 years old and older. The widespread

78 deployment of the electronic frailty index, which automatically grades frailty using data available
79 in the primary care electronic medical records (15), supported this national effort.

80 Innovative care models involving a combination of the above components of care have
81 emerged to grow the capacity for more comprehensive care of frail older adults, (16) and to
82 improve health and social outcomes (17). Greater integration of care among healthcare
83 professionals of different disciplines and across settings for frail older adults has reduced
84 unnecessary hospitalisations (18) and supported the maintenance of functional mobility over a 12-
85 month period (19). A systematic review of integrated or coordinated care found that

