138 community volunteers are screening for frailty amongst older adults. Community nurses have also
139 started to perform rapid and targeted geriatric and frailty assessments at neighbour-based nursing
140 posts (31). However, the link between frailty assessments and the wider network of community
141 care providers needs to be strengthened. To address this gap, the Singapore Ministry of Health
142 provided funding to test the effectiveness of a new programme for frail adults aged 65 years old
143 and older – the GSH –, which will be piloted by five sites. While there is no national consensus on
144 the tools for identifying or grading frailty, the Ministry has specified the use of the Clinical Frailty
145 Scale (CFS) (32) to support the enrollment of older adults living with mild, moderate or severe

146 frailty into the GSH programme. This study protocol will focus on the evaluation of these five
147 pilot sites. Due to geographical locations, the five pilot sites fall under the jurisdiction of two
148 different RHS in Singapore. Each site focuses on its existing strengths and resources to ride on or
149 build new partners within their RHS to provide community-anchored referral-gated geriatric care.
150 Through these partnerships, the GSH functions as a network of providers led by a core team of
151 acute hospital-based healthcare professionals (33). Each site acts as a consolidation point in the
152 community by actively receiving referrals from various services providers. All GSH sites share
153 the following goals:

- 154 • To provide early identification of frailty and offering comprehensive and coordinated care
155 in the community through collaborative working arrangements with partners, including
156 polyclinics, general practitioners (GPs), and community health and social service providers
- 157 • To provide CGAs to identify needs of frail older adults and to establish a care plan for each
158 individual patient
- 159 • To increase frail older adults access to essential services and transit across shared primary
160 care and other community-based providers more seamlessly
- 161 • To provide core services of geriatric assessments, nursing support, therapy service and case
162 management/care coordination
- 163 • To build capabilities by providing training to the primary care staff in identifying, caring
164 and managing frail older adults.

165 Despite these common goals, each GSH was designed differently to best harness their

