275 organisations including primary care clinics, and aged care facilities will be identified for another
276 round of focus group discussions. They may include the heads of doctors, nurses and
277 administrative staff who provided services within the new programme for at least six months.
278 Third, we aim to identify at least ten participants who receive care under the new model for at least
279 three months for the last round of focus group discussions. They must be able to take part in
280 conversation for at least 60 minutes. For individuals who do not have the capacity to participate,
281 his/her primary caregiver is eligible for participation.

282 We will conduct participant observations to better understand the processes involved by
283 shadowing 3 to 5 members of the staff over the course of one week per site to account for day-to-
284 day variations and job role differences.

285 Quantitative Evaluation

286 First, quality indicators will be developed to measure the processes of care for all individuals
287 enrolled into each programme. The relevant sub-populations accessing each care component will
288 form the denominator for computation of the indicators.

289 Second, we aim to recruit patients enrolled in the new programme. A target sample of 300
290 participants per site will be recruited. The sample was calculated based on the Barthel Index (100
291 points) – a scale to assess physical functioning, the key health outcome expected to improve as a
292 result of participation in the GSH. We computed the sample size for each participating site using
293 the dependent t-test to detect a small effect size of 0.2 (based on $\beta = .80$, $\alpha = .05$) (45). The result
294 was a minimum sample size of 156 per participating site. Allowing 20% rejection rate at the first
295 instance and a subsequent attrition rate of 30%, we would need to approach 300 individuals at the
296 first instance.

297 (Insert) Figure 1 Study sample for quantitative evaluation

298 Third, propensity score matching will be used to match programme enrollees and a
299 constructed comparator group. Both groups will be matched based on their probability of being
300 enrolled into the programme conditional on baseline covariates (46). The propensity score can be
301 used to mitigate selection bias in a non-randomised study. All programme enrollees will be
302 included as cases. Data on comparators will be derived from a Ministry of Health dataset

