303 containing information on the health status of community-dwelling older adults that were collected

304 as part of the government's efforts to communicate government policies to older adults and
305 connect them to relevant healthy ageing programmes.

306 **Study Procedure**

307 Qualitative Evaluation

308 Written informed consent will be obtained from all participants. They will first be invited to
309 complete a simple survey packet that consists of a basic demographic questionnaire and a scale to
310 assess their experiences in the programme. To obtain a thick description of the programme at each
311 site, possible explanations for why things are such, and to identify key strengths and challenges of
312 implementation at each site, interview guides were developed based on 12 out of 15 factors
313 identified by Kodner and Kyriacou (2000) to be integral to the development and implementation
314 of integrated care (40). We chose this framework as it provided sufficient components to evaluate
315 the different GSH site holistically. The framework also provides structure to evaluate similarities
316 and differences in the operations of the different GSH sites.

317 The 15 factors include patient screening, multidisciplinary assessment, primary care,
318 comprehensive service package, network relationships, care management, continuity and coverage
319 of care, seamlessness/ease of transitions, teamwork, information sharing, focus on continuum of
320 care, strategic planning, governance and management, funding mechanism and system outcomes.
321 Of the 15 factors, the research team deliberated and identified 12 that were key to understanding
322 the GSH implementation across the four sites. We renamed one of the factors “focus on continuum
323 of care” as “patient-centred care” to reflect work done by providers to align with patients’ needs
324 and preferences but at the same time to better differentiate this factor from “continuity of coverage
325 and care” or having control over transitions between services and providers. A brief description of
326 their relevance to the GSH is outlined in Table 3 below.

Table 3. Factors integral to understanding GSH implementation

Factors	Brief description
Patient screening	Identification of frail older persons in the community.
Multidisciplinary assessment	Performing a comprehensive, multidimensional patient evaluation and developing a care plan to meet identified needs.

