420 the progress of the programme. Baseline characteristics will be described with mean and SD for
421 continuous variables, and number and percentage for categorical variables.

422 For survey-collected outcomes, Generalised Linear Models (GLM) will be used to allow us
423 to make inferences about the population when accounting for the within-subject correlation.

424 A propensity score conditional upon observed covariates will be computed for all cases
425 (Figure 1). Variables will include sociodemographic information, disease burden measured by the
426 Charlson Comorbidity Index (55), and physical functional status. We will match 2 comparators to
427 1 case using nearest-neighbour matching. In a Monte Carlo simulation, the mean squared error for
428 a 2:1 match was minimised in 84 percent of the simulations compared with 68 percent for a 1:1
429 match (56). Nearest neighbour matching based on a calliper of 0.01 of the standard deviation of
430 the propensity score will be used (46, 57). Only cases and comparators with propensity scores

431 falling within a common support region range will be included in the analysis to ensure
432 comparability of the two groups.

433 In the multivariable regression analysis of count data, Poisson distribution or Negative
434 Binomial distribution (variance greater than the mean) will be used. Negative Binomial regression
435 can be used for over-dispersed count data when the conditional variance exceeds the conditional
436 mean. GLM will be used for modelling non-normally distributed continuous data such as length
437 of stay and healthcare cost. The results will be presented as incidence-rate ratios (IRRs). All
438 analyses will be performed using Stata/SE 16.1(58), with the level of significance set at 5%.

439 Integration of qualitative and quantitative data

440 Qualitative and quantitative data are collected concurrently and analysed separately. In the
441 final interpretation of the data, we will bring together and triangulate the results from the various
442 coordinated parts (59). Findings from each component of a study will be listed to allow the
443 evaluation team to look for convergence in findings, offer complementary information on the same
444 issues and to highlight discrepancies (60). Findings from interviews, focus group discussions and
445 participant observations will be used to contextualise quantitative process indicators and for

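### Programme entry is gated on frailty, but the plan names no frailty restriction on comparators and no frailty variable in the propensity score, so matched comparators are likely to be less frail

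*Combined protocol and SAP*

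**What the plan says.** **Who becomes a case.** Under Geriatric Services Hubs, "the Ministry has specified the use of the Clinical Frailty" "Scale (CFS) (32) to support the enrollment of older adults living with mild, moderate or severe" frailty. Table 1 gives age 65 or over and CFS 5-7 for every site. Study Sample (Quantitative Evaluation) makes every enrollee a case.

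**Who becomes a comparator.** The same section continues: "included as cases. Data on comparators will be derived from a Ministry of Health dataset" "containing information on the health status of community-dwelling older adults that were collected" during government outreach on policies and healthy-ageing programmes. No age or frailty criterion is stated for this pool.

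**What they are matched on.** Data Analysis (Quantitative evaluation): "Variables will include sociodemographic information, disease burden measured by the" Charlson index, and physical functional status. Matching is 2:1 nearest neighbour, with a calliper of 0.01 SD of the propensity score and a common-support rule.

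**Design and claims.** Evaluation Design calls the utilisation and cost comparison retrospective, pre-post and matched. Data Analysis names Poisson, negative binomial and GLM models reported as IRRs, but no group-by-period term and no prior-utilisation covariate. Strengths and limitations says that matching will bring the groups close at baseline and minimise selection bias; it concedes unmeasured confounding in general terms, without naming frailty.

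**The concern.** A propensity score models the chance of enrolment, and here the variable that decides enrolment is not among those named. The calliper and common-support rule act only on the score, so they cannot balance or reveal anything the listed variables miss. Standardised differences on those variables could look excellent while the groups differ in frailty.

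The Background says that frail older adults are more prone to disability, hospitalisation and death, so leftover frailty in the enrolled group raises its acute use and cost whatever the programme does. This is the only controlled comparison in the evaluation, and objective 3 rests on it. For emergency admission and cost, where the plan hopes for reductions, a real benefit could be hidden. For rehabilitation and ambulatory services, where the plan predicts an increase, the same imbalance could create or enlarge the predicted result.

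**Working it through.** The documents state no effect size or sample size for the matched comparison, so there is no planned figure to reproduce. What follows sizes the bias under stated assumptions.

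**Input from the documents.** The Background reports the prevalence "of frailty in Singapore ranged from 5.7% to 6.2% with corresponding 37% to 46% for pre-frailty". I take 6% as one value for the frail share p of the comparator pool. The frail share of the Ministry dataset itself is not given, so 15% and 30% are also tried.

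**Assumptions not in the documents.**
- Frailty F is standard normal in the pool; the frail are those with F > c, where c = Φ⁻¹(1 − p).
- Cases are a random draw from the frail.
- The listed covariates act as one score X with correlation r to F; r runs from 0.6 to 0.9.
- The utilisation rate is proportional to exp(bF), with b = ln(1.3) = 0.2624 per SD.
- The pool is large enough for exact matching on X, and the programme has no effect.

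**Formula.** A matched comparator with score X has F distributed as N(rX, 1 − r²). Averaging exp(bF) over cases and over their matches, the normal terms cancel and leave

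spurious IRR = Φ(b − c) / Φ(b·r² − c).

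The mean frailty gap is (1 − r²)·φ(c)/p.

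**Worked case, p = 6%, r = 0.7.** c = 1.5548.
- Numerator: Φ(0.2624 − 1.5548) = Φ(−1.2924) = 0.0981.
- Denominator: Φ(0.2624 × 0.49 − 1.5548) = Φ(−1.4262) = 0.0769.
- Spurious IRR = 0.0981 / 0.0769 = 1.28; frailty gap about 1.01 SD.

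**Spurious IRR, no programme effect, rate ratio 1.3 per SD:**

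| Frail share of pool | r = 0.6 | r = 0.7 | r = 0.8 | r = 0.9 |
|---|---|---|---|---|
| 6% | 1.36 | 1.28 | 1.19 | 1.09 |
| 15% | 1.27 | 1.21 | 1.14 | 1.07 |
| 30% | 1.19 | 1.15 | 1.10 | 1.05 |

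Simulated 2:1 nearest-neighbour matching agrees to about 0.02.

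**Non-frail share of matched comparators** (same model, numerical integration), at r = 0.6, 0.7, 0.8, 0.9:
- 6% pool: 81%, 74%, 64%, 48%
- 15% pool: 69%, 62%, 52%, 38%
- 30% pool: 55%, 48%, 40%, 29%

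**What this does to a real effect.** If the true IRR were 0.80 (assumed), the observed value is 0.80 × the table entry. At r = 0.7 that is 0.80 × 1.28 = 1.02 with a 6% pool, 0.80 × 1.21 = 0.97 at 15% and 0.80 × 1.15 = 0.92 at 30%. At r = 0.9 and 6% it is 0.80 × 1.09 = 0.87.

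**Pre-post contrast.** If F and b are constant over time, the same factor appears in the pre-period ratio, and a group-by-period contrast gives 1.28 / 1.28 = 1.00. If the gradient steepens, it does not cancel. With 1.3 per SD before and 1.5 after (p = 6%, r = 0.7), the post-period factor is 1.43, and 1.43 / 1.28 = 1.12 remains.

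**The case against.** Five points on the other side carry weight.

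1. **The design is pre-post.** Under a constant frailty effect, a group-by-period contrast removes the bias completely. This stands in principle, and the table above describes a post-period comparison only. But Data Analysis does not specify that contrast, and it would not remove diverging trajectories between frailer and less frail people.

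2. **Physical function and age are strong proxies.** True, and r gives them credit. Even r = 0.9 leaves 1.05 to 1.09. The actual r is unknown.

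3. **The plan may already handle frailty.** The variable list is introduced in open terms, and Figure 1 on the study sample is not available to this review. The visible text does not commit to a frailty filter or covariate. That supports asking for the commitment; it does not prove that none was intended.

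4. **The Ministry pool may be frailer than the community figure.** The quoted prevalence comes from population studies using various tools. It is neither a CFS 5-7 figure nor a description of this dataset. The bias shrinks at 15% and 30% but does not vanish.

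5. **A frailty measure may not exist for comparators.** The protocol says that "community volunteers are screening for frailty amongst older adults", but not that the results enter the Ministry dataset, and it notes no national agreement on tools. The linked data are described as sociodemographics, the survey (enrollees only), service use, cost and mortality, which may not support a deficit-count index.

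A reader might infer that comparators will be mostly non-frail and that every IRR is biased against the programme. The documents support neither. The first depends on r and on the pool's frail share: at 30% frail and r = 0.7 or above, most matches are frail. The second fails for the hypothesised rise in appropriate services, where the bias runs in the programme's favour.

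**Conclusion.** The point holds as a gap between the enrolment rule and the comparator plan. CFS 5-7 decides who is a case; the visible text neither applies a frailty criterion to the pool nor names frailty in the score, so matched comparators are likely to be less frail. For a post-period comparison the spurious IRR is about 1.05 to 1.36 over the grid above, enough to erase an assumed 20% reduction at the 6%, r = 0.7 setting but not at every setting. Those figures rest on assumed values for r, the pool's frail share and the 1.3 gradient. The direction is firmer: upward for utilisation and cost, unless the listed variables capture frailty almost fully or a pre-post contrast cancels a constant difference. The general caveat about unmeasured confounders does not cover this, because the enrolment criterion is known and Table 4 already records CFS for referred patients.

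This should be fixed. Confidence is medium, because the content of the Ministry dataset and Figure 1 cannot be seen.

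**What to change.** 1. Before matching, restrict the comparator pool to people aged 65 or over who are frail on whatever frailty measure the Ministry dataset or linked records hold. Add that measure to the propensity score for both groups and report its standardised difference alongside the others.
2. Write the pre-post contrast into Data Analysis as a group-by-period term, using pre-period utilisation from the linked records. Comparators have no enrolment date, so define an index date for them.
3. If no frailty measure is available for comparators, say so in Strengths and limitations in place of the claim of close baseline matching. State the expected direction separately: against the programme for avoidable use and cost, in its favour for appropriate services.

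**Cost.** No new patients or visits. If a frailty field exists, this is a filter, one covariate and one model term. The price is a smaller comparator pool and some unmatched enrollees. The documents do not confirm that such a field exists, and any field may not equal CFS 5-7, so some residual imbalance should be expected.

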To assess the process of development and implementation of the new programme	
• To examine the perceptions, roles, responsibilities, and experience in developing and implementing each programme• To understand the workflow from the perspective of each profession for each of the new programmes• To improve competency of primary care providers in identifying, caring and managing geriatric patients in the community• To explore differences in contextual factors across the five sites that have influenced implementation experiences and outcomes• To understand care recipients' experiences in receiving frailty care in the community	Qualitative - Semi-structured in-depth interview with key policy and programme decision-makers Qualitative - Semi-structured focus group discussions with health and social care professionals and care recipients Qualitative – Participant observations Quantitative – Longitudinal monitoring of process indicators
To assess the health, quality of life, and user experience effects on care recipients and the burden of care on primary caregivers	
• To compare outcomes between baseline, 3- and 6-months for each programme	Quantitative - Pre-test post-test design using survey-based data collection
To determine the impact on healthcare utilisation and cost impact of the new programme	
• To assess the use of healthcare services and costs between participants and non-participants for each programme	Quantitative - Retrospective cohort design with propensity score matched comparators

208
209 Based on the components the sites are funded for (Table 1), we will evaluate the GSH
210 program conducted by Ng Teng Fong General Hospital (NTFGH) based on evaluation objective 1
211 – to assess the process of development and implementation of the new programme. The focus is
212 on competency building, with the funding being utilised to cover the time spent by trainers and
213 trainees. In addition, the funding will not be used to cover healthcare costs incurred by patients.

214 Based on these considerations, evaluation objectives 2 and 3 would not be representative of the
215 results of the program. The remaining four sites will be evaluated on all three evaluation objectives
216 as their funding structures includes subsidising the healthcare costs of patients.

217 **Qualitative Evaluation**

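### Each site is sized on one Barthel test at alpha .05, but the plan compares two follow-ups at 5% and names no lead contrast, joint test or sidedness

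*Combined protocol and SAP*

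**What the plan says.** In the Combined protocol and SAP, Study Sample (Quantitative Evaluation), the Barthel Index is introduced in the words "points) – a scale to assess physical functioning, the key health outcome expected to improve as a" (the sentence goes on to credit programme participation). The size of each site is computed from "the dependent t-test to detect a small effect size of 0.2", with alpha .05 and a figure of .80 that is printed as beta. The result "was a minimum sample size of 156 per participating site" is then inflated for 20% refusal and 30% attrition to 300 people approached. No time point is attached to this test, and the text does not say whether it is one- or two-sided.

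Table 2 gives the survey objective as "To compare outcomes between baseline, 3- and 6-months for each programme". The text below the table takes one of the five sites out of this objective: "The remaining four sites will be evaluated on all three evaluation objectives".

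The Data Analysis section (Quantitative evaluation) specifies generalised linear models that allow for within-subject correlation. It names no contrast, no lead time point and no joint test of time. Its only rule on error is "analyses will be performed using Stata/SE 16.1(58), with the level of significance set at 5" per cent. Table 5 lists nine survey outcomes and does not mark any of them as primary or secondary.

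**The concern.** The sample size assumes one test of the key outcome at each site. The analysis leaves two natural tests of that outcome, baseline to 3 months and baseline to 6 months, and does not say which one answers the question. An analyst who tests both at 5%, and counts either as evidence of change, works at a higher error rate than the one used to size the site.

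The survey component has no control group, and the Discussion says the evaluation will help determine each programme's effects on health outcomes. The site-level Barthel result is therefore likely to be read as evidence of effectiveness. If the contrast is chosen after the data are seen, a reader cannot tell a planned result from a selected one.

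**Working it through.** **Inputs.** From the Study Sample section: standardised paired effect 0.2, alpha .05, 156 evaluable per site, 20% refusal, 30% attrition. The printed .80 is read as power, because that reading reproduces the 156. From Table 2: two follow-ups. Assumed: the correlation r between the two Barthel contrasts, which the documents do not give. If the three measurements have equal variance s² and equal pairwise correlation c, the two changes share a baseline, with covariance s²(1 − c) and variance 2s²(1 − c) each, so r = 0.5. The range shown is 0.3 to 0.7.

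**Step 1. Reproduce the 156.** Paired t-test, noncentrality 0.2 × √n, n − 1 degrees of freedom. At n = 156 the noncentrality is 2.498.

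| Test | Critical t at n = 156 | Power at 156 | Smallest n for 80% |
|---|---|---|---|
| One-sided 5% | 1.655 | 80.0% | 156 |
| Two-sided 5% | 1.975 | 69.9% | 199 |

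The plan's figure is reproduced exactly by the one-sided test and not by the two-sided test.

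**Step 2. Inflation.** 156 / (0.8 × 0.7) = 278.6, so 279, which the plan rounds up to 300. Approaching 300 gives 300 × 0.8 × 0.7 = 168 completers. Power at 168 is 82.6% one-sided and 73.2% two-sided.

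**Step 3. Error at one site if both follow-ups are tested at 5%.** With no true change, treat the two test statistics as bivariate normal with correlation r. The chance of at least one significant result is 1 − P(|Z3| ≤ 1.96 and |Z6| ≤ 1.96) for two-sided tests, and 1 − P(Z3 ≤ 1.645 and Z6 ≤ 1.645) for one-sided tests.

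| r | Two-sided 5% each | One-sided 5% each |
|---|---|---|
| 0.3 | 9.5% | 9.3% |
| 0.5 | 9.1% | 8.8% |
| 0.7 | 8.3% | 8.0% |

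The ceiling, with independent contrasts, is 1 − 0.95² = 9.75%. At r = 0.9 the two-sided figure is still 7.0%. In the two-sided column, the chance of a false finding in the improvement direction at r = 0.5 is 4.5%, against 2.5% for a single test. In the one-sided column the whole 8.8% is in that direction.

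**Step 4. Two ways back to 5% per site.** With one named lead contrast, the error is 5% and the sample size is unchanged. Keeping both contrasts with a Bonferroni split (alpha .025 each) needs 199 evaluable one-sided or 241 two-sided for 80% power. Naming one contrast is the cheaper route.

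**The case against.** The strongest reply is that nothing in the plan is contradicted. The alpha in the sample size and the 5% in the analysis are both per-test levels, and they agree. Comparing outcomes across baseline, 3 and 6 months also fits one joint test of time in the repeated-measures model, for which the site-level error would be 5%. The Barthel Index is already singled out as the key outcome. The five sites run differently designed programmes, each sized on its own. The integration section speaks of looking for convergence across components, not of declaring success on any one result.

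Most of this stands, and it rules out stronger readings that a reader might infer:

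- *A stated error rate is broken.* The plan never claims a rate for a family of tests, so none is broken.
- *About 32% for at least one false Barthel result across four sites.* This treats four separate programmes as one family and assumes a claim that the plan does not make. Part of it comes only from counting sites: one test per site already gives 1 − 0.95⁴ = 18.5%.
- *97.5% over 9 × 2 × 4 = 72 tests.* This assumes independence among outcomes measured in the same patients, and no conclusion in the plan rests on any one of 72.
- *One pooled test, or a Holm correction across sites, is required.* Pooling would displace the per-programme question that the study was sized for. Holm's strictest step (alpha .0125) would cut site power at 156 to 59% one-sided or 49% two-sided. These are trade-offs for the sponsor, not corrections of an error.

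The reply does not supply the missing choice. A joint test is possible but is not specified, and it is not the single pre-post test on which the 156 rests.

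**Conclusion.** The point holds in a limited form. The plan does not say which Barthel contrast is the test that each site was sized for. If both follow-ups are tested at 5%, the chance of a false Barthel finding at a site is about 9% (8.3% to 9.5%). That figure depends on the assumed correlation of 0.7 to 0.3 and on either follow-up being allowed to count. Under a joint test of time, or one pre-named contrast, it returns to 5%.

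The unstated sidedness is a separate gap that needs no assumption about correlation. The planned 156 is a one-sided figure, and a two-sided reading leaves power near 70%. Both gaps can be closed with a few sentences before analysis. Neither invalidates the design.

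**What to change.** In Study Sample and in Data Analysis (Quantitative evaluation):

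1. Name one lead Barthel contrast per site as the test at 5%. Baseline to 6 months, the last follow-up, is one example; the documents do not dictate the choice. Say that this contrast is estimated from the within-subject model.
2. Report the other follow-up as supportive, with a 95% interval.
3. State the sidedness of the lead test, in the same words in both sections.
4. Label the other eight Table 5 outcomes secondary, and flag their p-values as unadjusted.
5. State that each of the four sites is a separate question, with its own lead test.

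Cost: items 1, 2, 4 and 5 need no more participants. If 6 months is chosen, a change seen only at 3 months cannot by itself support a site-level effectiveness claim. Item 3 is free if the one-sided test is kept and justified. If the test is two-sided, the sponsor either accepts about 73% power with 168 completers or raises the target to 199 evaluable, which means approaching 199 / (0.8 × 0.7) = 355.4, so 356 per site.
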